14.1. Study Medication

The investigational medicinal product (IMP) bemcentinib must be stored in a secure location. Accountability for study treatment is the responsibility of the investigator. The investigator/designee must ensure that the IMP will only be dispensed to patients in accordance with the protocol and that any unused IMP will be disposed of or, if unopened, returned in accordance with the written instructions of the sponsor.

Study staff should refer to the sponsor's Directions for Handling and Administration (DHA) document for specific instructions regarding the handling, storage, dispensing and destruction of the IMP.

Bemcentinib has been manufactured according to appropriate Good Manufacturing Practice (GMP) standards. Bemcentinib will be labelled in compliance with GMP Annex 13 requirements, Food and Drug Administration (FDA) requirements and local regulatory guidelines.

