14.1.2. Cytarabine and Decitabine

All patients in Part B2 and Part B5 will receive subcutaneous low-dose cytarabine.

Name: Cytarabine

Brand name: Ara-C

Active Substance: Cytosine Arabinoside

Pharmaceutical form: Solution for injection

Route of administration: Subcutaneous

Investigational Medicinal Product Status: Non-IMP

ATC code: L01BC01

Cytarabine will have commercial packaging and labels in accordance with its marketing authorization. It will be purchased by the participating hospital via their normal purchasing procedure and will not be reimbursed by BerGenBio ASA.

All patients in Part B3 will receive intravenous decitabine per standard practice.

Name: Decitabine

Brand name: Dacogen

Active Substance: Decitabine (5-aza-2'-deoxycytidine)

Pharmaceutical form: Solution for injection

Route of administration: Intravenous

Investigational Medicinal Product Status: Non-IMP

ATC code: L01BC08

Decitabine will be packaged and labelled in the standard manner according to the current marketing authorization by the manufacturer. It will be purchased by the participating hospital via their normal purchasing procedure and will not be reimbursed by BerGenBio ASA.

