15.2.3. All Events

All events must be assessed to determine the following:

- If the event meets the criteria for an SAE as defined in Section 15.2.2
- The severity of the event as defined in Section 15.3.1
- The relationship to bemcentinib as defined in Section 15.3.2

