15.3.2. Assessment of Causality

The investigator will assess the causality of the AE with respect to the IMP according to the following guidance:

Unrelated The Adverse Event is clearly unrelated to bemcentinib

Unlikely	The Adverse Event is doubtfully related to bemcentinib
Possible	The Adverse Event may be related to bemcentinib
Probable	The Adverse Event is likely to be related to bemcentinib
Definite	The Adverse Event is clearly related to bemcentinib

If in the opinion of the investigator an SAE is considered not related an alternate etiology must be provided. The causality assessment given by the investigator should not be downgraded by the sponsor. If the sponsor disagrees with the investigator's causality assessment, both the opinion of the investigator and the sponsor should be provided with the report.

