### 5.8.1 Adverse events

The number and percentage of patients reporting TEAEs will be tabulated by MedDRA preferred term and system organ class, and summarized by CTCAE grade also. All AEs commencing prior to dosing with study medication will be excluded from the tabulation but will be fully listed.

A subject with more than one occurrence of the same adverse event in a particular system organ class will be counted only once in the total of those experiencing adverse events in that particular system organ class. If a subject experiences the same adverse event at more than one severity, or with more than one relationship to study drug, the most severe rating or the stronger causal relationship to study drug will be given precedence. Any missing severity, causality, or outcome will not be imputed and classed as unknown.

An overall summary classifying subjects with events according to seriousness, severity, maximum relationship to BGB324, and maximum CTCAE grade will also be presented.

Related events are defined as events that are definitely, possibly or probably related to study medication or with an unknown relationship.

Treatment-Emergent AEs are any AEs that start or worsen after first dose of study drug until 28 days following the last dose. AEs with partial onset dates will be assumed to have the latest possible onset date (while accounting for stop date) for determining treatment emergence, but no formal imputation will be done. AEs that have missing onset dates will be considered to be treatment-emergent, unless the stop date is known to be prior to the first administration of BGB324.

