#### 5.8.1.1 Subsets

- Non-serious adverse events will be presented by dose level (part A) or treatment group (parts B), system organ class and preferred term

- Related (BGB324) adverse events will be presented by dose level or treatment group, system organ class and preferred term.
- Related (Cytarabine) adverse events will be presented by system organ class and preferred term. (Part B2 only)
- Related (Decitabine) adverse events will be presented by system organ class and preferred term. (Part B3 only)
- Related (Other Anti-Cancer Medications) adverse events will be presented by dose level or treatment group, system organ class and preferred term.
- Serious adverse events will be presented by dose level or treatment group, system organ class and preferred term
- Related (BGB324) serious adverse events will be presented by dose level or treatment group, system organ class and preferred term.
  - Related (Cytarabine) serious adverse events will be presented by system organ class and preferred term. (Part B2 only)
  - Related (Decitabine) serious adverse events will be presented by system organ class and preferred term. (Part B3 only)
  - Related (Other Anti-Cancer Medications) serious adverse events will be presented by dose level or treatment group, system organ class and preferred term.
  - Serious adverse events will be presented by dose level or treatment group, system organ class, preferred term, and maximum CTCAE grade.
- Adverse events leading to discontinuation will be presented by dose level or treatment group, system organ class and preferred term.
- Adverse events  $\geq$  Grade 3 will be presented by dose level or treatment group, system organ class and preferred term.
  - Related (BGB324) adverse events  $\geq$  Grade 3 will be presented by dose level or treatment group, system organ class and preferred term.
  - Related (Cytarabine) adverse events  $\geq$  Grade 3 will be presented by system organ class and preferred term. (Part B2 only)
  - Related (Decitabine) adverse events  $\geq$  Grade 3 will be presented by system organ class and preferred term. (Part B3 only)
- The most frequent MedDRA preferred terms ( $\geq 10\%$  subjects in the overall safety population restricted to each part) will be presented by dose level or treatment group.
- Separate listings will be produced for DLTs, SAEs, related (all 3 types) AEs, discontinuations due to AEs, and events of  $\geq$  Grade 3 severity.

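### The protocol asks for AE causality to bemcentinib only, but the SAP tabulates causality to other drugs and counts blanks as related, so those tables could be inflated unless the eCRF collects causality for each drug

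*SAP*

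**What the plan says.** **What sites are asked to record.** Protocol 15.2.3 lists what must be determined for every event. The only causality item is "The relationship to bemcentinib as defined in Section 15.3.2". Section 15.3.2 opens with "The investigator will assess the causality of the AE with respect to the IMP according to the following guidance", and each of its five categories, from unrelated to definite, is worded in terms of bemcentinib. Protocol 14.1 identifies the investigational product: "The investigational medicinal product (IMP) bemcentinib must be stored in a secure location". Cytarabine and decitabine each carry the entry "Investigational Medicinal Product Status: Non-IMP" in 14.1.2. No section of the supplied protocol tells a site to rate an event against either of them, or against any other anti-cancer drug.

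**What the SAP does with a blank.** SAP 5.8.1 says "Any missing severity, causality, or outcome will not be imputed and classed as unknown" and, shortly afterwards, "Related events are defined as events that are definitely, possibly or probably related to study medication or with an unknown relationship". The definition speaks of study medication in general and does not vary by drug.

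**What the SAP tabulates.** SAP 5.8.1.1 plans AE, SAE and Grade 3 or higher summaries for events related to cytarabine and to decitabine. For cytarabine the entry reads "Related (Cytarabine) adverse events will be presented by system organ class and preferred term. (Part B2 only"; decitabine is limited to B3 in the same way. For the remaining drugs it says "Related (Other Anti-Cancer Medications) adverse events will be presented by dose level or treatment group, system organ class and preferred term", with a matching SAE summary.

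**The concern.** Part B's primary objective is the safety of bemcentinib alone and in combination. Tables by attributed drug are there to separate bemcentinib toxicity from that of the partner drug. Counting an unknown relationship as related is a cautious rule for the investigational product, because it avoids understating that product's toxicity. For a background drug the same rule does the opposite of what the table is for: it assigns to that drug events that nobody attributed to it.

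The blanks are also foreseeable. Even if the eCRF has a causality field for each drug, the protocol gives no instruction and no scale for completing the fields for the background drugs.

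**Working it through.** The plan states no figure here, so there is nothing to reproduce. The check follows the rule through the text and then sizes it.

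**Step 1, the chain.** Causality to a background drug is not requested (protocol 15.2.3, 15.3.2). If the field is blank, the value becomes unknown (SAP 5.8.1). Unknown counts as related (SAP 5.8.1). The event then enters the related table for that drug (SAP 5.8.1.1).

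**Step 2, the outputs exposed** (SAP 6.3.3.1):
- cytarabine and decitabine, six tables: 14.3.1.2.4, 14.3.1.2.5, 14.3.1.3.4, 14.3.1.3.5, 14.3.1.5.3 and 14.3.1.5.4;
- other anti-cancer medications, four tables: 14.3.1.2.6.1, 14.3.1.2.6.2, 14.3.1.3.6.1 and 14.3.1.3.6.2.

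**Step 3, size.** Let m be the share of AEs with no causality rating for the drug, and r the share rated possible, probable or definite among those that are rated. The documents give neither, so both are assumptions.

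- Share counted as related under the SAP rule: m + (1 − m)r.
- Share counted as related if blanks are kept apart: (1 − m)r, with m shown as not assessed.

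At an assumed r = 0.3:

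| m | SAP rule | Blanks kept apart |
|---|---|---|
| 0 | 30% | 30% |
| 0.05 | 0.05 + 0.95 × 0.3 = 33.5% | 28.5% |
| 0.5 | 0.5 + 0.5 × 0.3 = 65% | 15% |
| 0.9 | 0.9 + 0.1 × 0.3 = 93% | 3% |
| 1 | 100% | 0% |

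**Step 4, how much must be blank before nearly everything is related.** Setting m + (1 − m)r = 0.9 gives m = (0.9 − r)/(1 − r). This is 0.89 for r = 0.1, 0.86 for r = 0.3, 0.80 for r = 0.5 and 0.67 for r = 0.7. Between two thirds and nine tenths of the ratings would have to be missing.

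**Step 5, other anti-cancer medications.** These tables run over every dose level and treatment group in the Safety Population. SAP 4.3.2 allows some AML patients on monotherapy to add such drugs after two cycles, so some patients will have taken one and others not. The SAP has no not-applicable category and no limit to recipients. If the field is left blank for non-recipients, m is at least their share of all AEs, however well the field is completed for recipients.

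**Unit.** The formula counts events. SAP 5.8.1 tabulates patients, counts repeats once and lets the stronger relationship take precedence, without saying where unknown ranks. The percentages above show how the rule behaves; they do not predict table entries.

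**The case against.** The strongest counter-argument is that the SAP's authors evidently expected causality to be recorded by drug. SAP 5.8.1.1 refers to three types of relatedness, and SAP 6.4 plans separate listings for bemcentinib, cytarabine, decitabine and other anti-cancer medications (16.2.7.3 to 16.2.7.6). If the eCRF holds those fields and they are well completed, the distortion is small: 33.5% against 30% at m = 0.05 and r = 0.3. If the fields do not exist, the tables may simply not be producible, which is a different fault from inflation.

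Three further points carry weight. The SAP covers four country protocols, and the US version it cites is 9.0. The supplied protocol is US version 10.0, so the bemcentinib-only wording is checked for one version only. The SAP's definition refers to study medication, which arguably does not reach other anti-cancer drugs, although the SAP offers no other definition for those tables. And the cytarabine and decitabine tables are already confined to cohorts that receive the drug, so the recipient problem mainly concerns the other anti-cancer tables.

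A reader might also infer that these tables decide whether one agent of a combination may be continued alone. They do not. Protocol 9.3.2 makes that an investigator's decision during treatment, and end-of-study tables cannot inform it.

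These points limit the size of the problem. They do not remove the mismatch between what the protocol asks for and what the SAP tabulates, or the literal effect of the missing-data rule.

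**Conclusion.** The mismatch and the rule both stand on the text. The supplied protocol requests causality to bemcentinib only, and the SAP tabulates causality to other drugs and turns a blank into a related event. The background-drug tables could therefore be inflated, by anything from a few percentage points to every event, depending on an eCRF that is not shown.

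It is tempting to go further and say that nearly every AE will be reported as related to the background drug. The documents do not support that. It would need 67% to 89% of ratings to be missing for r between 0.7 and 0.1, and the planned by-drug listings suggest that fields exist. The result rests on the assumed m and r, on one of the country protocols, and on reading the SAP definition as applying to every related table. The all-AE tables are not affected, and for the bemcentinib-related tables the cautious rule is appropriate and can stay.

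**What to change.** **SAP 5.8.1 and 5.8.1.1:**
1. Replace the general reference to study medication with a definition of related for each named drug.
2. Keep the rule that unknown counts as related for bemcentinib.
3. For cytarabine, decitabine and other anti-cancer medications, count only possible, probable or definite as related. Limit each table to patients who received that drug before AE onset, and show events not assessed in their own column.
4. Include B5 in the cytarabine-related summaries. Section 5.8.1.1 marks them as B2 only, although B5 patients also receive cytarabine and SAP 5.1 plans to summarise B2 and B5 together for some AE outputs.

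**Protocol 15.2.3 and 15.3.2:** for combination patients still on treatment, state that the relationship to the combination agent is recorded on the same five-category scale. This cannot help Part B3, which protocol 16.8 reports as fully completed. For B5 it is useful only if item 4 is also made.

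**Cost:** a few sentences in the SAP and one in the protocol, plus one causality field at any site not already completing it. No visits or patients are added. The one drawback is a not-assessed column for events already collected.

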15.2. Monitoring and Reporting Events

15.2.1. Adverse Events

Any AE experienced by a patient between signing the informed consent form (ICF) and 28 days after the last administration of bemcentinib is to be recorded in the eCRF regardless of the severity and causality of the event, although only events considered to be related to treatment need to be recorded between the last administration of bemcentinib and the end of the 28-day follow up period. If bemcentinib-related toxicities continue beyond the Follow-up period, patients will be followed until all bemcentinib-related toxicities have resolved to Grade ≤1, stabilized or returned to baseline.

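### The SAP's rule for partial AE onset dates has no cap at last dose + 28 days, so some AEs that may have begun in the window can be classed as non-emergent

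*SAP*

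**What the plan says.** SAP 5.8.1 sets both ends of the window: "Treatment-Emergent AEs are any AEs that start or worsen after first dose of study drug until 28 days following the last dose". For a partly known onset date it says: "AEs with partial onset dates will be assumed to have the latest possible onset date (while accounting for stop date) for determining treatment emergence", and adds "but no formal imputation will be done". The assumed date therefore serves only to classify the event, and the stop date is the only limit named.

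The sentence that follows deals with onset dates that are wholly missing: "AEs that have missing onset dates will be considered to be treatment-emergent", unless the AE is known to have stopped before the first administration. Protocol 16.4.2 has the same rule for missing dates and none for partial dates.

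The only exclusion from tabulation that SAP 5.8.1 spells out is at the start of the window: "All AEs commencing prior to dosing with study medication will be excluded from the tabulation but will be fully listed". The exclusion at the end follows from the definition, because the section tabulates treatment-emergent events.

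On what is recorded, protocol 15.2.1 covers "Any AE experienced by a patient between signing the informed consent form (ICF) and 28 days after the last administration of bemcentinib", but it relaxes this after treatment: "only events considered to be related to treatment need to be recorded between the last administration of bemcentinib and the end of the 28-day" follow-up period. Protocol 15.2.2 collects SAEs with a suspected relationship to bemcentinib without a time limit.

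**The concern.** Taking the latest possible date is inclusive at first dose: an event that could have begun on treatment is counted. At the other end of the window the same choice works in the opposite direction. It assumes the date most likely to fall after last dose + 28, and unless the stop date pulls it back the event is classed as non-emergent.

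The result is inconsistent. Suppose an ongoing AE has a known onset year and nothing more. It can be left out of the tables, whereas the same AE with a blank onset date would be counted, so more information can remove an event. SAP 5.5 avoids this for medications, where partly and fully missing start dates share one inclusive rule.

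Safety and tolerability is the Part B primary objective, and treatment-emergent AEs are the first safety endpoint listed in SAP 3.1. The events at risk are those with no stop date in the window. After last dose they are mainly events judged related, because only those must be recorded.

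**Working it through.** The documents give no figure on this point, so there is none to reproduce. The check counts calendar dates.

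**Inputs.** Window end = last dose + 28 days (SAP 5.8.1). Assumed onset = last day of the known month, or 31 December if only the year is known (SAP 5.8.1, latest possible date).

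**Assumptions.** The AE is ongoing, so no stop date limits the assumed date. It does not worsen in the window. Last-dose dates are uniform over a 365-day year, and onsets are uniform over the period stated. There is no cap other than the stop date. An AE is lost if its assumed onset is later than last dose + 28.

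**1. Day missing, onset in the month of last dose.** Month-end must fall more than 28 days after last dose. That needs a last dose on day 1 or 2 of a 31-day month, or on day 1 of a 30-day month: 7 × 2 + 4 × 1 = 18 of 365 last-dose dates (4.9%).

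**2. Day missing, onset in the last L days on drug.** The lost pairs of last-dose date and onset date number 1 + 2 = 3 in each 31-day month and 1 in each 30-day month: 7 × 3 + 4 × 1 = 25. The share lost is 25 / (365 × L):
- L = 21: 25 / 7,665 = 0.33%
- L = 84: 25 / 30,660 = 0.08%
- L = 180: 25 / 65,700 = 0.04%

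**3. Day missing, onset 1 to 28 days after last dose.** Let the window close on day j of a month with n days. If j < n, the min(j, 28) onsets in that month are lost. If j = n, none is lost. Summed over j, this gives 462 for a 31-day month, 434 for a 30-day month and 378 for February. The total is 7 × 462 + 4 × 434 + 378 = 5,348, out of 365 × 28 = 10,220. The share lost is 52%.

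**4. Year only.** If onset is in the year of last dose, the AE is lost for every last dose up to 2 December: 336 of 365 dates (92%). If onset is in an earlier year, 31 December of that year precedes last dose and the AE is kept. For onset in the last L days on drug, the share lost is the sum of min(t, L) over t = 1 to 336, divided by 365 × L:
- L = 21: (210 + 21 × 316) / 7,665 = 6,846 / 7,665 = 89%
- L = 84: (3,486 + 84 × 253) / 30,660 = 24,738 / 30,660 = 81%
- L = 180: (16,110 + 180 × 157) / 65,700 = 44,370 / 65,700 = 68%

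**5. First-dose boundary.** With the day missing in the month of first dose, month-end is never before first dose, so the AE is kept for 365 of 365 dates.

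A 366-day year gives nearly the same results.

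**6. Whole window, day missing.** If onsets were spread evenly from first dose to last dose + 28, the share lost would be about 28 / (days on drug + 28) × 0.523:
- 21 days: 28/49 × 0.523 = 30%
- 63 days: 28/91 × 0.523 = 16%
- 90 days: 28/118 × 0.523 = 12%
- 180 days: 28/208 × 0.523 = 7%

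Step 2 shows that almost none of this loss comes from AEs that began on drug.

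**The case against.** The strongest reply is that the rule is already bounded in practice. AE recording under protocol 15.2.1 ends 28 days after last bemcentinib, the same day as the window. On that reading an ordinary recorded AE has no possible onset after the window, so nothing can be pushed out. This is a sensible way to read the two documents together, but the SAP does not say it, and a programmer working from SAP 5.8.1 would find only the stop date as a limit. The reading also fails for related SAEs, which protocol 15.2.2 collects without a time limit.

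The other replies stand, and they narrow the point:

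- AEs are recorded at every visit, and visits are frequent in Cycles 1 and 2 and then once per 21-day cycle. Onset dates with the month unknown should be uncommon, so the 68% to 89% applies to a group of unknown and possibly very small size.
- A reader might take the 30% to 7% in step 6 as the general loss when only the day is missing. The even spread behind it places 28/49 = 57% of AEs after last dose for a patient with 21 days on drug, although only related events must be recorded then. On-treatment onsets are lost in 0.33% of cases or fewer.
- A reader might also infer that the error always lowers the AE count. It does so only at the end of the window. At first dose the rule can add screening-period AEs to the tables.
- A misclassified AE remains in the AE listings, an AE that worsens inside the window still qualifies, and one that stopped inside the window is protected by the stop-date clause.

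**Conclusion.** The rule as written can give a wrong classification, and it is inconsistent with the rule for missing dates in the next sentence. The defect is confined to AEs with no stop date inside the window whose partial date runs past last dose + 28. These are mainly year-only dates, and day-missing dates in the calendar month that runs past the window's close.

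For those cases the share lost is about 68% to 89% of onsets in the last 180 to 21 days on drug (year only), and about 52% of onsets 1 to 28 days after last dose (day missing). Both rest on the uniformity assumptions above and on the absence of any cap but the stop date.

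The documents do not support the broader reading that the rule generally removes ongoing AEs from the treatment-emergent tables. With only the day missing, on-treatment onsets are almost always kept. How many AEs have partial onset dates is not stated, so no effect on the tables can be claimed. The change is worth making because it is cheap and concerns the rule that decides what enters the main safety tables.

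**What to change.** Replace the SAP 5.8.1 sentence on partial onset dates with:

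*An AE with a partial onset date is treatment-emergent if any date consistent with the known parts of the onset date, and not after the stop date, lies from first dose to 28 days after last dose.*

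Treatment at first dose does not change, and the clause on worsening stays as it is. Applied to a wholly missing onset date, the sentence gives the existing rule: emergent unless the AE stopped before first dose. In-window AEs wrongly excluded because of a partial date fall to zero by construction.

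The cost is one SAP sentence and one line of derivation code. The downside is that a few AEs that truly began after the window may be counted. It would also help to report the number of AEs with partial onset dates, so that readers can see how far the rule matters.
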